 - Participants will be asked to investigate their dasiglucagon infusion set and consider replacing it, check for any occlusions along the fluid path, and check to make sure that the cartridge is not empty.
- Alarms will sound and a visual alert will appear on the Dexcom CGM app if CGM glucose is > 250 mg/dl.
 - Participants will be trained to test their BG with the study glucometer and the ketone level with the study ketone meter (provided) in response to such an alarm and take necessary measures to treat the hyperglycemia.
 - Participants will be trained on troubleshooting for various scenarios that could lead to persistent or severe hyperglycemia. For instance, hyperglycemia could be due to true hyperglycemia (caused by a missed insulin dose or a failed infusion set for example) or inaccurate CGM readings.
 - The first step in responding to severe or persistent hyperglycemia according to the CGM will be to perform a fingerstick BG and, if necessary, ketone measurement.
 - If the BG measurement is not consistent with the CGM readings, the participant will calibrate the CGM.
 - If the BG measurement is consistent with the CGM readings:
 - Participants will be asked to investigate their insulin infusion set and consider replacing it, check for any occlusions along the fluid path, and check to make sure that the cartridge is not empty.
 - Study staff will recommend the participant continue to monitor their BG until it returns to normoglycemia, and to contact study staff with any questions or concerns.
 - If ketones ≥ 0.6 mmol/L are present:
 - Participants will be advised to change their pump infusion set and will be reminded that the BP should dose insulin accordingly.
 - Study staff will recommend the participant continue to monitor their ketone levels and BG every 60 minutes until ketones return to < 0.6 mmol/L and BG is < 180 mg/dl, and to contact study staff with any questions.
 - If participants experience persistent hyperglycemia lasting more than 2 hours, they will be instructed to contact study staff for consideration of infusion set replacement and/or correction insulin according to the above protocol.

Remote Monitoring Protocol

- All remote monitoring will be the same in both study arms.

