- Real-time remote telemetric monitoring for biochemically severe hypoglycemia or persistent hyperglycemia will be performed by the study staff 24 hours a day. There will be at least one provider (MD, NP, or PA) on call at all times. Additional study staff members may assist with on call duties. A staff member will make contact with participants as necessary and help them troubleshoot any issues that may arise.
- When an alert comes in, a study staff member will call the participant. Depending on the circumstances, they may call locations the participant is known to frequent (e.g. usual work location) or they may be dispatched to make contact with the participant (if the location is nearby and reaching the location would be no risk to the safety of staff member or violate employment rules).
- If study staff are not able to get in contact with the participant, they may contact the designated contact. These designated contacts should have access to where the participant may be sleeping if necessary.
- Remote monitoring is only possible when the participant has Verizon network coverage and data can be transmitted to the cloud service. There may be times when a participant enters an area where Verizon coverage is not available. We may also encourage participants to connect to public but secure wireless networks if they are having trouble connecting to cellular service.
- An alert will be generated if remote monitoring indicates that a participant is offline.
 - If there are no indications of device malfunction as the cause for lost connectivity, the glucose level is in safe range, and a participant chooses to remain in an area with poor network coverage, we will instruct the participant to check the iLet display or CGM at least every 20 minutes for alert icons and to be aware that we are unable to monitor for severe lows or highs at this time.
 - We will call the participant every 2 hours to check on safety and device function until remote monitoring is restored.
 - The same rules will be used for checking in when the participant in both study periods.
- The remote monitoring system will generate an alarm if the CGM glucose is < 50 mg/dl for 15 minutes.

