 - Study staff will verify the participants are aware of the hypoglycemia and taking action to treat it. Participants will be reminded of the protocol for hypoglycemia, and the study provider will ensure they understand and will follow study procedures. Participants will be encouraged to follow up with any questions or concerns. All contact with the participants in response to hypoglycemia alarms will be documented.
 - In the case of a low threshold alarm with no response from the participant and no success in locating them or their designated contact, the site principal investigator will be immediately informed. If remote monitoring shows ongoing hypoglycemia, a decision may be made to dispatch emergency medical services to the locations the participant is known to frequent.
 - Remote monitoring for hypoglycemia will be the same in both study periods.
- The remote monitoring system will generate an alarm if the CGM glucose is > 300 mg/dl for 90 minutes.
 - Participants will be reminded of the protocol for prolonged hyperglycemia, and the study provider will ensure they understand and will follow study procedures. Participants will be encouraged to follow up with any questions or concerns. All contact with the participants in response to hyperglycemia alarms will be documented.

- Remote monitoring for hyperglycemia will be the same in both study periods.

VI. d. iv. Visit Procedures

Day 1 Visit:

Participants may be trained on the operation of the all study devices in a group setting or may be trained one-on-one. Both the participant and the study staff must be satisfied that the participant is comfortable with the operation of all study devices before he/she begins the study. Additional training sessions may be arranged as needed.

- Participants will complete their baseline psychosocial questionnaires
- Their body weight, heart rate and blood pressure will be documented
- Blood will be drawn for a chemistry panel and complete blood count, and a baseline assessment of anti-drug antibodies.
- Study staff will review any changes in the participant's medical history or medications to ensure continued eligibility, and any adverse events that may have occurred since their screening visit. Study staff will specifically ask subjects if they had any infusion site reactions or other skin irritation in the past 7 days, and will document any reactions.

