- Participants will be trained on the insertion and use of the Dexcom G5 CGM. Participants will insert their own CGM sensor and study staff will confirm they are doing it correctly.
- Study staff will review all study procedures and policies (including the use of the Dexcom G5, the Contour Next One, the Precision Xtra ketone meter, and the iLet device) and the upcoming visit schedule.
- The Dexcom G5 will be calibrated by the participant using the Ascensia Contour Next One SMBG glucometer, and study staff will confirm they are doing it properly.
- Participants will be trained on the use of the iLet.
- The control algorithm will be initialized with the participant's current weight
- The participant will remove his/her own insulin infusion pump and the participant will set up and start the iLet under the supervision of study staff. Participants will be instructed to not take any further insulin outside of the iLet throughout the study.
- The staff will confirm that the iLet is functioning properly prior to discharging the participant.
- All participants will be given Dexcom G5 CGM sensors, an Ascensia Contour Next One SMBG meter with test strips, ketone meter with strips, insulin, dasiglucagon for the bihormonal study arm, a glucagon emergency kit, an iLet, iLet pigtail adapters and Contact Detach infusion sets (an alternate infusion set may be supplied if the subject is known not to do well with the Contact Detach).

Day 7/Day 1 Visit:

- There may be no washout between the two study arms or the washout period may be up to 7 days.
- At the end of the first 7-day arm, subjects will return to the clinic and answer the post questionnaires for the study arm.
- The body weight, heart rate and blood pressure of the subject will be documented
- Blood will be drawn for a chemistry panel and complete blood count.
- Study staff will review any changes in the participant's medical history or medications to ensure continued eligibility, and any adverse events that may have occurred since their last study visit. Study staff will specifically ask subjects if they had any infusion site reactions or other skin irritation in the past 7 days, and will document any reactions.
- The iLet and the study glucometer will be downloaded. The memory of the iLet will be wiped and

it will be re-initialized for the next study period.

- Participants will replace their CGM sensor and calibrate when prompted if they haven't already.

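### No ketone level requires a call to study staff, so high ketones at CGM 251–300 mg/dl may prompt no required contact for about two hours

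*Combined protocol and SAP*

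**What the plan says.** The relevant rules are in section VI.d.iii (Local Alarms and Remote Monitoring Protocol) and section VI.d.iv (Visit Procedures).

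- **Testing.** When the CGM alarm sounds above 250 mg/dl, participants are trained to measure blood glucose and "the ketone level with the study ketone meter (provided) in response to such an alarm".
- **Ketone branch.** The only action level is 0.6 mmol/L. At or above it, participants are advised to change the set, are reminded that the device should adjust insulin, and recheck every 60 minutes "until ketones return to < 0.6 mmol/L and BG is < 180 mg/dl, and to contact study staff with any questions".
- **Duration rule.** If hyperglycemia persists beyond 2 hours, "they will be instructed to contact study staff for consideration of infusion set replacement and/or correction insulin according to the above protocol".
- **Telemetry.** "The remote monitoring system will generate an alarm if the CGM glucose is > 300 mg/dl for 90 minutes". Staff then call the participant.
- **Lost connectivity.** "We will call the participant every 2 hours to check on safety and device function until remote monitoring is restored".
- **Outside insulin.** "Participants will be instructed to not take any further insulin outside of the iLet throughout the study". The general policies in VI.d.iii make exceptions for technical faults and complete iLet failure.

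Section VI.d.vii encourages contact for significant nausea or any vomiting. Section VI.d.vi, on the response to hyperglycemia, mentions neither ketones nor the 2-hour rule. The only other ketone figure is above 1.5 mmol/L, in the DKA definition (sections X.b and X.c). There it is one of four joint criteria for classifying an event and not an action level.

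**The concern.** A ketone reading just above 0.6 mmol/L and one several times higher lead to the same steps and the same discretionary contact. Participants measure ketones, but no ketone result escalates the response. The required contacts depend on glucose duration, glucose level or connectivity, and the symptom trigger is only an encouragement.

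This matters because the alarm procedure itself names a failed infusion set as a possible cause of hyperglycemia. The ketone branch relies on the device to dose insulin. Section I.b describes that dosing as based on glucose data and insulin absorption kinetics, with no ketone input. Within the alarm response, correction insulin is mentioned only in the 2-hour bullet, as something staff would consider. A provider's decision may therefore be needed, and no ketone reading asks for one. What is at stake is how early a provider hears of a participant with high ketones. No treatment comparison is at stake.

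**Working it through.** This is a check of text. The plan states no figure to reproduce, and it gives no rate of raised ketones from which to estimate events.

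**Step 1. List each route to contact and what sets it off.**

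| Route | Set off by | Uses the ketone value? | Required? |
|---|---|---|---|
| Ketone branch | Ketones ≥0.6 mmol/L | Yes, one tier | No, only if the participant has questions |
| Duration rule | Hyperglycemia >2 hours | No | Yes, participant instructed to call |
| Telemetry | CGM >300 mg/dl for 90 minutes | No | Yes, staff call |
| Offline check | Lost connectivity | No | Yes, staff call every 2 hours |
| Nausea or vomiting | Symptoms | No | No, encouraged |

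Ketone levels that require a call: 0.

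**Step 2. Find the case that the required routes reach last.** Take CGM at 251–300 mg/dl, the participant online, no nausea or vomiting, and no device fault found.

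- The telemetry alarm does not fire, because CGM is not above 300 mg/dl.
- The offline calls do not start.
- The symptom route does not apply.
- The duration rule remains, at more than 2 hours.

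**Step 3. Put times on it.** Assume that the 2-hour clock starts at the >250 mg/dl alarm and that ketones are first measured then. At 60-minute spacing, readings fall at 0, 60 and 120 minutes. The first two precede the 2-hour mark and the third coincides with it. The first required contact is therefore about 2 hours after the alarm, whatever the ketone values.

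**Step 4. Vary the assumption.** The duration rule gives no glucose level for persistent hyperglycemia. If the clock starts at a lower glucose, before the alarm, the wait after the alarm is shorter than 2 hours. If hyperglycemia resolves within 2 hours, the duration rule requires no contact, however high the ketones were. About 2 hours is thus a reading under one plausible clock and not a fixed property of the plan.

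**The case against.** The strongest reply is that the participant is well covered. A provider is on call at all times and telemetry runs around the clock. Participants check the infusion set, fluid path, cartridge and device operation, and a technical fault requires an immediate call to technical support. Designated contacts are trained to recognize symptoms of hyperglycemia and to know when to call staff or emergency services. The wording of the ketone branch, in which staff advise and recommend, may also imply that staff are already involved. All of this stands as mitigation. None of it makes a ketone value a reason to call, and no bullet in the ketone branch makes staff involvement a requirement.

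A reader might infer more, and the documents do not support it:

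- *That raised ketones never lead to a required call.* The 2-hour rule in the same procedure applies at any ketone level.
- *That ketone testing is optional.* One step says the first response "will be to perform a fingerstick BG and, if necessary, ketone measurement". But the same procedure already trains participants to test ketones at every >250 mg/dl alarm, so the qualifier can sensibly mean a test not yet done. Replacing the alarm-triggered test with one conditional on a confirmed fingerstick could even reduce testing.
- *That ketone data are lost.* Section VII.e.ii does not list ketone readings, and at the end of the first arm "The iLet and the study glucometer will be downloaded". But that list also omits the chemistry panel, blood count and anti-drug antibodies, which are collected at visits. The final visit downloads the study meters in the plural, and only the iLet's memory is said to be wiped between arms. No endpoint uses home ketone values.
- *That the comparison of configurations is biased.* Alarm settings, remote monitoring and the response to hyperglycemia are the same in both arms.

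**Conclusion.** The point holds as a narrow, minor safety-procedure improvement that the sponsor could adopt. The ketone branch has a single tier, and no ketone value requires contact. At 251–300 mg/dl, online and without nausea or vomiting, the first required contact may come about 2 hours after the alarm. That figure assumes that the clock starts at the >250 mg/dl alarm and that no device fault prompts an earlier call. The documents give no basis for saying how often this would happen in 10 completers over two 7-day periods. Neither the primary endpoint nor the time below 54 mg/dl is affected.

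**What to change.** In Local Alarms (section VI.d.iii):

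1. Keep the ketone test at every >250 mg/dl alarm.
2. Keep the set change and hourly rechecks at 0.6 mmol/L or more.
3. Keep the >2-hour contact rule.
4. Add an immediate call to the on-call provider above a stated ketone level. Above 1.5 mmol/L is one example, because the figure already appears in the DKA definition. It is not an action level there, so the exact value is the sponsor's clinical choice.
5. Cross-reference this sequence from section VI.d.vi.

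The cost is a few lines of protocol and training text and a few extra calls to a provider who is already on call. Ketone meters and strips are already handed out at the Day 1 visit, and no change to the statistical analysis is needed.

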- A urine pregnancy test will be performed in pre-menopausal female volunteers. If the test is positive the volunteer will be informed of the result and the visit will be ended.
- Height, weight, heart rate and blood pressure will be measured. An EKG will be performed.
- If the volunteer is not excluded based on historical criteria, blood pressure, EKG or urine pregnancy test, blood will be drawn for hemoglobin A1c, and fractionated metanephrines if applicable. A study MD or NP will review the case report form to determine subject eligibility. If subjects are not eligible to continue in the study the results of abnormal tests will be reported to the subjects and to a health care provider of their choosing.
- A questionnaire will be administered to assess impaired awareness of hypoglycemia.
- Subjects who have been screened and are eligible can participate without having to be re-screened for a period of 3 months. The study staff should verbally confirm that there have been no health events that would make them ineligible at every study visit, and rescreen subjects for eligibility if it has been greater than three months.
- Once enrolled, subjects will identify up to 2 designated contacts (caregivers/family

members/friends) who are willing to serve as an emergency contact for the participant, requiring them to answer phone calls and check on the participants wellbeing as needed. If possible, they would also be an appropriate person to answer questionnaires about their experiences and attitudes towards the subject's diabetes and the impact of the bionic pancreas.

- Study staff will confirm the designated contacts are able to provide informed consent and are willing and able to serve as an emergency contact, and can recognize and treat hypoglycemia. If possible, they will confirm the contacts also have an appropriate relationship with the study participants to answer these questionnaires. Informed consent will be obtained from these contacts, and study staff will collect basic demographic information (age, sex, race/ethnicity) as well as contact information.
- All designated contacts will be trained in the symptoms of hypoglycemia and response to severe hypoglycemia, including the administration of glucagon. They will also be trained to recognize the symptoms of hyperglycemia, and when to contact study staff and local EMS.

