- Study staff will review all study procedures and policies (including the use of the Dexcom G5, the Contour Next One, and the iLet) and the upcoming visit schedule.
- The control algorithm will be initialized with the participant's current weight. The participant will set up and start the iLet under the supervision of study staff. Participants will be instructed to not take any further insulin outside of the iLet throughout the study.
- The staff will confirm that the iLet is functioning properly prior to discharging the participant.
- All participants will be given additional supplies as needed.

Final Day 7 Visit:

- At the end of the second 7-day arm, subjects will return to the clinic and answer the post questionnaires for the study arm.
- The body weight, heart rate and blood pressure of the subject will be documented.
- Blood will be drawn for a chemistry panel and complete blood count.
- An EKG will be performed. This EKG will be assessed relative to the baseline EKG to identify any potential changes.
- Any changes to medications or medical history and any adverse events that may have occurred since their last study visit will be documented. Study staff will specifically ask subjects if they had any infusion site reactions or other skin irritation in the past 7 days, and will document any reactions.
- The iLet and the study meters will be downloaded.
- All equipment will be collected and cleaned. The Dexcom G5 transmitter will be cleaned using the validated cleaning and disinfecting procedures.
- A study provider will review the last few hours of glucose trend data and insulin and dasiglucagon on board from the iLet, and assist the participants in resuming their usual diabetes management.

Follow Up Visits

- Subjects will return for a follow up visit 10 days (± 3 days) after the final day 7.
 - Any changes to medications or medical history and any adverse events that may have occurred since their last study visit will be documented. Study staff will specifically ask subjects if they had any infusion site reactions or other skin irritation since their last study visit, and will document any reactions.
 - Blood will be drawn for anti-drug antibodies.
 - If the EKG on the final Day 7 visit showed any changes relative to the baseline EKG, an additional EKG will be performed at this follow up visit.
- Subjects will return for a second follow up visit 25 days (± 4 days) after the final day 7.

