- CGMG (CGM glucose) every five minutes from the Dexcom CGM
- All fingerstick BG measurements taken by the subject (meter download)
- Average glucose target used
- Insulin total daily dose from bionic pancreas download
- Glucagon total daily dose from bionic pancreas download
- Timing of meal announcements and size of meals announced from bionic pancreas download
- Time subjects were not under bionic pancreas control
- List of technical faults associated with the bionic pancreas including cause and resolution
- Body weight after each study arm
- Blood pressure after each arm
- Heart rate after each arm
- Skin reactions, if any, after each arm
- EKG after completion of the second arm, and at the first follow up visit if applicable
- Information collected from the daily email survey:

- Number of reported hypoglycemic events requiring carbohydrate intervention
- Total grams of carbohydrates taken to treat hypoglycemia
- Number of severe hypoglycemic events (defined as subject required assistance to treat)
- Mean nausea severity from VAS
- Number of unscheduled insulin cartridge/infusion set changes
- Number of unscheduled glucagon cartridge/infusion set changes
- Alcohol use (mean drinks per day)
- Exercise duration and exposure (duration X intensity)
- Data from questionnaires about attitudes and expectations regarding the bionic pancreas at baseline and on day 7 of each arm.

VIII. Risks and Discomforts

Subjects may experience mild discomfort associated with the insertion of infusion sets and the Dexcom CGM sensor into the SC tissues. The risk of discomfort due to insertion of infusion sets and sensors may be greater than in their lives outside the trial because more infusion sets and sensors are required than are used in usual care.

There is a risk of hypoglycemia. This risk is expected to be less than the risk during the subjects' lives outside of the trial based on data from earlier trials. All of our previous studies have shown that hypoglycemia is significantly reduced in all configurations of the bionic pancreas when compared with usual care.

There is a risk of hyperglycemia. This risk is expected to be less than the risk during the subjects' lives outside of the trial based on data from earlier trials. All of our previous studies have shown that hyperglycemia is significantly reduced in all configurations of the bionic pancreas when compared with usual care.

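### No EKG is scheduled at the end of the first arm, so participants randomised to bihormonal first have none at the end of dasiglucagon exposure

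*Combined protocol and SAP*

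**What the plan says.** The baseline EKG is taken at screening (VI.d.i): "Height, weight, heart rate and blood pressure will be measured. An EKG will be performed".

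The Day 7/Day 1 visit closes the first arm (VI.d.iv): "At the end of the first 7-day arm, subjects will return to the clinic and answer the post questionnaires for the study arm". Its safety items are vital signs ("The body weight, heart rate and blood pressure of the subject will be documented"), a chemistry panel, a blood count, adverse events and skin reactions. No EKG is listed. On the gap before the second arm, the section says: "There may be no washout between the two study arms or the washout period may be up to 7 days".

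The Final Day 7 visit closes the second arm and adds the EKG: "An EKG will be performed. This EKG will be assessed relative to the baseline EKG to identify any potential changes".

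The only later EKG is conditional (VI.d.iv, Follow Up Visits): "If the EKG on the final Day 7 visit showed any changes relative to the baseline EKG, an additional EKG will be performed". It falls at the first follow-up visit: "Subjects will return for a follow up visit 10 days (± 3 days) after the final day 7".

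The data list in VII.e.ii agrees with the visit schedule. Weight, blood pressure, heart rate and skin reactions are collected after each arm, but the EKG entry reads "EKG after completion of the second arm, and at the first follow up visit if applicable".

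**The concern.** The Final Day 7 EKG is an individual check against baseline. In a participant who receives bihormonal second, it is read at the end of dasiglucagon exposure. In a participant who receives bihormonal first, it is read at the end of the insulin-only week. The same procedure therefore answers a different question in each sequence, and the protocol gives no reason for the difference.

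The conditional repeat does not close the gap, because it depends on the same late reading. In bihormonal-first participants, a change present when dasiglucagon stopped but gone by Final Day 7 would not be recorded and would not trigger a repeat.

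The protocol itself treats cardiac rhythm as a safety matter. Exclusion criterion 12 removes people whose EKG suggests a raised risk of malignant arrhythmia, and criterion 13 bars drugs linked to torsades or bradycardia for the whole dosing period. Criterion 5 means that no participant has had dasiglucagon before. The only completed use of dasiglucagon in this system that the background describes (I.e) lasted up to 8 hours; here exposure lasts 7 days. Section VIII allows for unknown risks of the drug. What is at stake is whether every participant has an EKG at the end of that exposure.

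**Working it through.** The plan states no figure on this point, so there is none to reproduce. The check is one of visit timing.

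**Inputs**
- Arm length: 7 days, two arms in random order, dasiglucagon in the bihormonal arm only (III.a).
- Washout: 0 to 7 days (VI.d.iv, Day 7/Day 1 Visit).
- First follow-up: 10 ± 3 days, that is 7 to 13 days, after Final Day 7 (VI.d.iv, Follow Up Visits).
- Expected completers: 10 (V.a).
- Allocation ratio: not stated (VI.d.ii); 1:1 is assumed below.

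**Days from the end of dasiglucagon to each EKG, current plan**

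Bihormonal first:
- Routine EKG = washout + second arm = (0 to 7) + 7 = 7 to 14 days.
- Conditional repeat = washout + second arm + follow-up interval: shortest 0 + 7 + 7 = 14 days, longest 7 + 7 + 13 = 27 days.

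Bihormonal second:
- Routine EKG = about 0 days.
- Conditional repeat = 7 to 13 days.

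| EKG | Bihormonal second | Bihormonal first, now | Bihormonal first, after the change |
|---|---|---|---|
| Routine | about 0 | 7–14 | about 0 |
| Conditional repeat | 7–13 | 14–27 | 7–14 (at Final Day 7) |

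The last column takes the routine EKG at Day 7/Day 1 and the repeat at Final Day 7, which is 7 + (0 to 7) = 7 to 14 days after dasiglucagon.

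**Number affected**
- At 1:1, 10 × 0.5 = 5 of 10 completers.
- If randomisation were simple (unblocked) 1:1, the number X who receive bihormonal first would be Binomial(10, 0.5). P(2 ≤ X ≤ 8) = 1 − (1 + 10 + 10 + 1)/1024 = 1 − 22/1024 = 0.979.

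**What the extra readings are worth (illustrative)**
- If no change is seen in n participants, the exact one-sided 95% upper bound on the rate of change is 1 − 0.05^(1/n). For n = 5 this is 45.1%; for n = 10 it is 25.9%.
- If the true rate were 20% (an assumed value), the chance of seeing at least one change is 1 − 0.8^n. For n = 5 this is 67%; for n = 10 it is 89%.

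**The case against.** The strongest reply is that the schedule is consistent and looks deliberate. The visit procedures and the data list agree, and the list separates what is collected after each arm from the EKG. Nothing says that the Final Day 7 EKG is meant to mark the end of dasiglucagon exposure; it could be an end-of-study check that all completers have at the same visit. That reading is weak: under III.c the study ends at the second follow-up visit, about 25 days after Final Day 7, so Final Day 7 is the end of treatment.

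The next reply is that little is at stake, and much of this stands. No passage says that dasiglucagon alters the EKG, and the specific risks in section VIII include no rhythm effect. EKG change is not a listed endpoint, and no inferential safety tests are planned (VII.d.iv). Persistent changes would still appear at Final Day 7. Symptoms would reach staff through the daily questionnaire and the adverse event review at visits, and heart rate is recorded after each arm. The loss is therefore confined to a change that is silent, does not show in heart rate and resolves within 7 to 14 days. An end-of-arm EKG is also not timed to a dose. With glucagon's time-to-peak of about 15–20 minutes (section I), very brief effects could be missed in either sequence. An upper bound of 25.9% is still wide.

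These points limit the importance of the gap but do not justify it. Heart rate cannot show the QT or ischaemic findings for which criterion 12 screens.

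Two objections concern the remedy. Moving the EKG takes the Final Day 7 reading away from bihormonal-first participants who show no change at the end of the first arm. That is a real, small loss, and keeping the reading avoids it. The other is that a mid-study EKG would need a rule for starting the second arm. X.b already lets the investigator withdraw a participant for whom continuing is judged unsafe, so no new clinical rule is required.

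**Conclusion.** The concern holds. Participants randomised to bihormonal first have no scheduled EKG at the end of dasiglucagon exposure, and the timing of the EKG relative to the drug is confounded with sequence. The timing figures follow directly from the visit schedule. The count of about 5 in 10 rests on an assumed 1:1 allocation.

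The consequence is a gap in individual safety assessment that should be closed because closing it is cheap. It does not bear on the study's operational or glycaemic conclusions.

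**What to change.** - **VI.d.iv, visits:** schedule the routine post-treatment EKG at the end of each participant's bihormonal arm. For bihormonal-first participants this is the existing Day 7/Day 1 visit, at the end of the first arm and before any washout. For bihormonal-second participants it stays at Final Day 7.
- **VI.d.iv, repeat EKG:** tie the trigger to that EKG. Place the repeat at Final Day 7 for bihormonal-first participants and leave it at the first follow-up visit for the others. If the sponsor prefers the first follow-up visit for everyone, the protocol should state that the lag is then 14 to 27 days in the bihormonal-first sequence.
- **VII.e.ii:** reword the EKG data item to match.
- **Optional:** keep the Final Day 7 EKG for all participants as well.

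The cost is a short amendment to these two sections. Both visits are already among the five paid study visits (XI), and the relocation leaves the routine total at 10 EKGs in 10 completers. Its one drawback is the lost Final Day 7 EKG in bihormonal-first participants with no change at the end of the first arm. The optional addition removes that drawback at the price of about 5 more EKGs (10 + 5 = 15, 1:1 assumed), at a visit that already takes place.
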